- Any condition or anatomy that makes treatment with the Linq Implant System infeasible
- Use of medications known to have detrimental effects on bone quality and soft-tissue healing (metabolic bone disease, induced or idiopathic)
- Prominent neurologic condition that would interfere with physical therapy
- Current local or systemic infection that raises the risk of surgery
- Patient currently receiving or seeking worker's compensation, disability remuneration, and/or involved in injury litigation.
- Patient is participating in an investigational study or has been involved in an investigational study within 3 months prior to evaluation for participation
- Patient with insurance coverage that does not cover the SI fusion*
- Implanted intrathecal pain pump

Withdrawal/Termination criteria:

- Patient's participation will only be withdrawn by their request. There are no criteria for termination of participation due to safety.

E. Specific methods and techniques used throughout the study

Study Design: The PainTEQ study is a prospective, multi-site, prospective, single arm study intended to collect clinical data outcomes data associated with the treatment of sacroiliac disease with the LinQ fusion procedure. Data will be collected using self-report measures including the visual analog scale (VAS) for pain assessment where the participant is asked to place a line perpendicular to the VAS line at the point that represents their pain intensity. Using a ruler, the score is determined by measuring the distance (mm) on the 10-cm line between the "no pain" anchor and the patient's mark, providing a range of scores from 0-100. Other self-report questionnaires will be administered including the Oswestry Disability Index (ODI) to measure low-back pain and disability, and the PROMIS 29 to measure physical, mental, and social health and well-being. The study team will also collect data including:

- Patient Satisfaction with Procedure
- Opioid consumption (Morphine Milligram Equivalents) at 1,3, 6, 12,18, 24 months.
- Serious adverse events and mortality as related to implantation of the device and events associated with recovery and rehabilitation
- Device related complications
- Satisfactory deployment (Defined as radiographic imaging of the implant within the SI joint. Procedure time
- Fluoroscopy time (in minutes)
- Blood loss
- Type of anesthesia (local; MAC; general)
- Patient demographics
 - Age
 - Gender
 - Race
 - BMI
 - Smoking (y/n)
 - Year of Pain

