 - Underlying diagnosis: degenerative sacroiliitis/sacroiliac joint disruption
 - Prior lumbar fusion (y/n)
 - Prior treatments (PT, FA, SIJ injection)

1. Timeline: Patients included in the study return for follow-up visits at 7-14 days, 1, 3 months, 6, 12, 18, and 24months post-treatment. Primary endpoint will be 6 month time point.
2. No randomization as treatment with the LinQ system will be performed regardless of whether the patient agrees to be in the research.

F. Risk/benefit assessment:

As appropriate, address the following parameters as each relates to the individual subject in the study.

1. Psychological risk: minimal, less than 1%
2. Social risk minimal, less than 1%
3. Potential benefit of participating in the study
 - a. To the individual subject and/or parent if any:

Improvement in the following domains:

 - a. Pain
 - b. Physical functioning
 - c. Emotional functioning
 - d. Patient global rating of improvement and satisfaction
 - e. Symptoms and adverse events
 - f. Patient disposition
 - b. To the population from which the subject is drawn: The study will provide

evidence to support a new treatment modality that is safe and effective. This

treatment modality also does not require repetition or multiple treatments unlike other treatments for sacroiliac joint dysfunction. It will also offer a salvage therapeutic option for patients who have failed other treatment modalities.

- c. To science, society, and humanity in general: Advancement of minimally invasive musculoskeletal techniques that may significantly reduce associated morbidity, mortality, and overall cost of treatment for chronic musculoskeletal related pain.

G. Location where study will be performed: Multisite

H. Collaboration: Multisite

I. Single IRB Review for a Multi-site study:

IRB local approval

J. Personnel who will conduct the study, including:

- 1. Indicate, by title, who will be present during study procedure(s): Study coordinator, attending physician, company representative, fellow physician (when available).
- 2. Primary responsibility for the following activities, for example:
 - a. Determining eligibility: PI, study attendings, senior trainees
 - b. Obtaining informed consent: Attendings at the study site including co-investigators, senior trainees at study site, and/or research coordinators
 - c. Providing on-going information to the study sponsor and the IRB: No Study Sponsors
 - d. Maintaining participant's research records: Research coordinator

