 - e. Completing physical examination: Attendings and trainees at study site
 - f. Taking vital signs, height, weight: Clinic staff
 - g. Drawing / collecting laboratory specimens: Not applicable
 - h. Performing / conducting tests, procedures, interventions, questionnaires: Attending physician and fellow physicians at study site
 - i. Completing study data forms: Research coordinator
 - j. Managing study database: Research coordinator

K. Adverse Event Monitoring

Adverse events and unanticipated problems will be ascertained and handled per standard of care as applies to any procedure. Problems that would be considered serious and reported to the IRB include infection, new skeletal fracture resulting from procedure, unanticipated post-operative admission, and neurologic injury and would be monitored for on an ongoing basis as per standard of care. The reporting timeframe would be within two weeks of incident to allow for appropriate additional diagnostic testing and treatment while maintaining study responsiveness to adverse events.

If patient experiences an adverse event or post-procedural problem, this will be treated per standard of care. This would include standard of care treatment of any related injury and potential device explanation. Patient may opt out of study at any time voluntarily. This would be monitored and discussed on an ongoing basis in the setting of an adverse event or post-procedural problem.

III. Subject Participation

A. Recruitment:

1. Potential study participants will come from the existing patient population of the investigators in each individual practice.

Recruitment can be performed by interventional pain providers and will be offered to anyone who is a candidate for the LinQ fusion procedure and meet the inclusion and exclusion criteria for the study. This research studies the LinQ system, a legally-marketed device, determined by that health care practitioner to be in the best interests of the patient. Patients will undergo treatment with the LinQ fusion procedure regardless of participation in the research. Therefore, the procedures being conducted because of the research are limited to data collection and the use of the LinQ system is not a research procedure.

B. Informed consent process and timing of obtaining of consent

The following study personnel may participate in the consent process: PI, co-Investigators, senior trainees, research assistants, and research coordinator.

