After it has been determined that the patient is a candidate for LinQ fusion procedure and they meet the inclusion and exclusion criteria, the patient will be offered the opportunity to participate in this study. An IRB approved consent form will be used for this study and obtained on all study patients prior to collecting any study related information or documentation. All questions that the potential study patient has will be addressed. Participation in the study is voluntary, study patients may withdraw at any time.

The clinician will determine if the patient has the capacity to proceed with informed consent. Only patients with capacity to proceed with informed consent will be included in study. Minors are not allowed to participate in the study. A legally appointed guardian, closest family member, or individual with power of attorney may not serve as a substitute.

Alternatives to Participation:

Alternatives to participation in research study is to not take part in this research.

C. Costs to Subjects:

The patient will not incur any costs because of research. The LinQ procedure will be performed regardless of participation in the research and standard charges will apply for the LinQ procedure. Eligibility criteria include insurance coverage for study procedure.

D. How new information will be conveyed to the study subject and how it will be documented:

New information regarding treatment options or significant results that may affect care will be conveyed and applied by standard of care guidelines. Standard of care includes appropriate, HIPAA compliant communication mediums. This information will be documented in the medical record as it applies to the patient's treatment per standard of care.

Payment, including a prorated plan for payment:

The subject will be paid \$250.00 at the 24 month visit for taking part in this research.

E. Payment for a research-related injury:

Study procedure is standard of care. Research-related injury will be handled as standard of care via accepted legal mechanisms, which include mediation, arbitration, or litigation for settlement.

IV. Data Collection and Protection

A. Data Management and Security:

Data will be collected from electronic medical record, during surgery, and self-report questionnaires. Confidentiality will be maintained by storing patient data on a cloud based secured, HIPPA compliant system. Identifiable data will not be sent outside any practice institution.

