B. Procedures to protect subject confidentiality:

Patient identifiers may be included in master spreadsheet for reference to clinical chart if need arises for further review. Data will be de-identified with master spreadsheet containing patient identifiers linked to generated ID. A secondary spreadsheet will be generated containing pertinent study measures linked to the generated ID. The study coordinator will serve as the honest broker or buffer between master and secondary spreadsheets.

V. Data Analysis and Reporting

A. Statistical and Data Analysis:

Statistical analysis will include paired t-test of quantitative measures such as VAS pain score, Oswestry Disability Index, PROMIS 29, and quantitative secondary outcomes. ANOVA regression analysis will be performed to identify potential correlates of improved outcomes measures and adverse outcomes. IBM SPSS Statistics will be utilized to perform the analysis. Interim analysis will be performed on an anticipated monthly basis by a statistician. At no time will identifying information be transferred.

B. Outcome Measures:

i. Primary Outcome Measures

1. Binary success failure composite end point. A subject was considered a success if all of the following criteria were met
 - a. Reduction from baseline VAS SIJ pain by at least 20 mm
 - b. Absence of device related serious adverse events,
 - c. Absence of neurologic worsening related to the lumbosacral nerve roots,
 - d. Absence of surgical reintervention (removal, revision reoperation or supplemental fixation) for SIJ pain

ii. Secondary Outcome Measures

1. Improvement in baseline in VAS from baseline at 6 months
2. Oswestry Disability Index at 6 months follow up
3. PROMIS-29 at 6 months follow up
4. Patient Satisfaction with PGIC
5. Morphine milligram equivalent usage at all time points

C. Study results to participants:

Once final analysis completed, debriefing report will be given at follow up appointment or via telephone call. If no further contact maintained, copy of published manuscript will be sent to patients. Purpose of this will be to debrief patients as to study results.

D. Visit Schedule

	At least 7 days prior to Baseline	(within 4 weeks of surgery)									
Informed Consent	X										
Inclusion / Exclusion Review	X	X									
Urine Pregnancy test (if required)	X										
Surgery Information			X								
VAS	X	X		X	X	X	X	X	X	X	
PROMIS-29		X		X	X	X	X	X	X	X	
ODI	X	x		X	X	X	X	X	X	X	
Patient Satisfaction					X	X	X	X	X	X	

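### The physicians who perform the intervention are also responsible for the questionnaires, so the self-reported pain score in the primary composite is open to courtesy reporting with no comparator to offset it

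*Protocol*

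**What the plan says.** Protocol II.J lists who is responsible for what. Item 2h covers treatment and assessment in a single line: "Performing / conducting tests, procedures, interventions, questionnaires: Attending physician and fellow physicians at study site". The research coordinator's tasks are maintaining research records (2d), managing the database (2j) and, in item 2i, "Completing study data forms: Research coordinator". Administering the outcome questionnaires is not among them.

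II.E describes the instruments as self-report. For the VAS, "the participant is asked to place a line perpendicular to the VAS line at the point that represents their pain intensity", and the mark is then measured with a ruler on a 0 to 100 scale.

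V.B makes the primary outcome a four-part composite. Its one efficacy component is "Reduction from baseline VAS SIJ pain by at least 20 mm"; the other three are absences of device-related serious adverse events, of neurologic worsening and of surgical reintervention. II.E item 1 sets the time: "Primary endpoint will be 6 month time point". The secondary outcomes include VAS change, ODI, PROMIS-29 and PGIC. II.B gives the design as single arm.

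On attendance, II.J item 1 lists "Study coordinator, attending physician, company representative, fellow physician (when available" as the people present at study procedures.

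**The concern.** The VAS is a subjective mark made by a patient who knows which treatment was given. If the form is handled by the physicians who recommended and performed that treatment, the patient may mark it more favourably than in private. A comparator collected in the same way would share that tendency, and much of it would cancel in the difference. Here there is no comparator, so a reporting shift at follow-up is indistinguishable from a treatment effect in both the 20 mm criterion and the paired t-tests. Enrolling more patients narrows the interval around the shifted value and does not move it back.

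The protocol fixes this arrangement itself by naming the responsible group. It is therefore not a detail that can be left to an analysis plan, and no analysis could recover the unshifted score.

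**Working it through.** **1. What the passages establish**

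| Question | Place | Answer |
|---|---|---|
| Who performs the intervention? | II.J 2h | Attending and fellow physicians |
| Who conducts the questionnaires? | II.J 2h | The same group, in the same line |
| Is the outcome self-reported? | II.E | Yes, the patient marks the VAS |
| Does it drive the primary outcome? | V.B; II.E item 1 | Yes, as one of four components, at 6 months |
| Is there a comparator? | II.B | No, single arm |
| Is private or independent completion provided for? | II.E, II.J, V | No |

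**2. The plan's own figure**

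The point rests on no stated figure. For completeness, the sample size in II.C reproduces: a paired t-test with effect size 0.5, two-sided alpha 0.05 and power 0.80 needs 33.37, rounded up to 34. Fifty enrolled with 20% loss leaves 50 × 0.8 = 40. The concern does not change these numbers.

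**3. Possible size (illustration)**

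The documents give no SD of VAS change, no expected mean change in this population and no size for a reporting shift. The assumptions are:

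- VAS reduction is normally distributed with SD 25 mm (20 and 30 mm are checked below).
- The differential shift b is 5 or 10 mm. A shift equally present at baseline and at follow-up cancels in the change score, so b is only the extra amount after treatment.
- The true mean reduction m runs from 20 mm, which lies on the threshold, to 41.5 mm. The upper value applies the 83% average reduction quoted in section I (20 patients, 3 months) to the minimum eligible baseline of 50 mm: 0.83 × 50 = 41.5.

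Formula: P(reduction ≥ 20) = Φ((m + b − 20) / SD).

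| m (mm) | b = 0 | b = 5 | b = 10 | Gain in points (b = 5, b = 10) |
|---|---|---|---|---|
| 20 | Φ(0) = 50.0% | Φ(0.20) = 57.9% | Φ(0.40) = 65.5% | 7.9, 15.5 |
| 30 | Φ(0.40) = 65.5% | Φ(0.60) = 72.6% | Φ(0.80) = 78.8% | 7.0, 13.3 |
| 41.5 | Φ(0.86) = 80.5% | Φ(1.06) = 85.5% | Φ(1.26) = 89.6% | 5.0, 9.1 |

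The range is about 5 to 16 points. The same formula at m = 20 gives, for SD 20, 59.9% and 69.1%, and for SD 30, 56.6% and 63.1%. At m = 41.5 it gives, for SD 20, 85.9% rising to 90.7% and 94.2%, and for SD 30, 76.3% rising to 81.1% and 85.3%. Across all three SDs the gain runs from about 5 to 19 points. It is smaller for a mean reduction above 41.5 mm.

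**4. From the VAS criterion to the composite**

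Success requires all four components. A patient moved over 20 mm becomes a success only if the other three are also met. If the shift leaves those three unaffected, the gain in composite success cannot exceed the gain in the VAS criterion.

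**The case against.** **Item 2h is thin evidence.** It is a bundled line under a heading on primary responsibility. It does not say that the individual implanter hands over the form, watches or reads it. The VAS is patient-marked and ruler-measured, and the coordinator completes the data forms. This stands as a limit: the protocol assigns responsibility to the treating group and does not describe the scene. It does not dispose of the point, because the questionnaires are assigned to that group and nothing separates the two tasks. The ruler limits scoring error but not what the patient chooses to mark.

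**The size is assumed.** This also stands. No SD or shift is documented, and a mean near 20 mm is where a shift has most effect. With the protocol's only efficacy figure applied to the minimum baseline, the gain is 5 to 9 points. Some expectation and courtesy effect would also remain if a coordinator from the same practice gave the form, so the fix cannot be credited with removing the whole shift.

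**The company representative.** A reader might infer that the manufacturer is present when patients score their pain. II.J item 1 lists a company representative, and III.A says that "the procedures being conducted because of the research are limited to data collection". The documents do not support that inference. III.A is about what is done because of the research and says that LinQ use is not a research procedure; it does not define the term used in item 1. Where the protocol uses *study procedure* elsewhere, it means the surgery: III.C speaks of insurance coverage for it, and III.E says "Study procedure is standard of care". Item 2h and the consent lists (II.J 2b, III.B) do not name the representative. The wording of item 1 is loose enough to need a clarification, and no more than that.

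**Conclusion.** The concern holds for the physicians. The protocol gives the group that performs the intervention responsibility for conducting the self-report questionnaires. It sets no safeguard on how these are completed and has no comparator to absorb a reporting shift. This is an exposure to bias and not evidence that bias will occur. It is worth correcting before data collection because it reaches the only efficacy component of the primary composite and most of the secondary outcomes, and because analysis cannot correct it afterwards.

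The size is unknown. The gain of about 5 to 16 points rests on normality, an SD of 25 mm, a differential shift of 5 to 10 mm and a true mean reduction of 20 to 41.5 mm. It concerns the VAS criterion and is an upper limit for composite success only while the other components are unaffected. It should be cited as illustration only. Sponsor presence at outcome collection is not established.

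**What to change.** Amend II.J item 2h to take the questionnaires out of the physicians' line. State that VAS, ODI, PROMIS-29 and PGIC, wherever scheduled, are self-completed in private, or given by the research coordinator already listed, before the physician sees the patient. Apply this at baseline and at every follow-up, so that both ends of the change score are collected in the same way.

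As a secondary clarification, state in II.J item 1 that the list refers to the implantation only, and that the company representative is not present when questionnaires are completed.

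The cost is a little more coordinator time per visit. Staffing, visit schedule, instruments and sample size stay as they are.

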Recently, an FDA approved posteriorly placed allograft into the mid-portion of the SI joint has shown significant promise as an alternative option to traditional or lateral SI fusion. The LinQ system is a minimally invasive, percutaneous, single incision technique for SI fusion. Utilizing a posterior approach eliminates the risk of spinal canal compromises and improves the overall safety profile. Additionally, using a single incision and avoiding screws reduces invasiveness and significantly reduces recovery times. A recent abstract presented by Pyles on 20 consecutive patients showed an average 83% reduction in pain at 3 months with no serious adverse effects or complications using the LinQ system[3]. The purpose of this multicenter, prospective, clinical series is to further establish the data, efficacy, and safety on the LinQ system for chronic Sacroiliac Joint Disease.

II. Research Plan and Design

A. Study Objectives:

The purpose of this post-market study is to gather evidence documenting the performance and clinical outcomes associated with treatment of sacroiliac disease with the LinQ fusion procedure.

B. Study Type and Design

Multicenter Center, Prospective, Single arm Clinical study

C. Sample size, statistical methods, and power calculation:

Anticipated study enrollment will be ongoing patients for registry.

Power calculation based on paired T test, Alpha 0.05, Beta 0.2, Power 0.8, Effect Size 0.5, two sided yielded sample size of 34 patients. Assuming a 20 percent loss to follow up or study exit rate, fifty patients would be sufficient to achieve study aims.

Statistical methods would include paired T tests for quantitative measures which include VAS score, Oswestry Disability Index, and Promis-29.

D. Subject Criteria:

Inclusion criteria:

- Age 21-70
- Patient has lower back pain for >6 months inadequately responsive to conservative care
- Patient has at least 3 of 4 physical examination maneuvers specific for the SI joint (FABER, Gaenslen test, Stork/Gillete, and Yoman)
- Patient has improvement in lower back pain numeric rating scale (NRS) of at least 50% after injection of local anesthetic into affected SI joint(s) with confirmed arthrogram, within 30-60 min from injection
- Degenerative sacroiliitis as SIJ mediated in the context of either radiographic evidence of SIJ degeneration, evident on computed tomography or Xrays or a history of prior lumbar fusion.

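### The paired t-tests fixed for 6-month VAS, ODI and PROMIS-29 leave the earlier scores of patients lost before month 6 out of the estimate, so improvement is overstated if poor responders leave

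*Protocol*

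**What the plan says.** - **Method, Protocol II.C:** "Statistical methods would include paired T tests for quantitative measures which include VAS score, Oswestry Disability Index, and Promis-29".
- **Method, Protocol V.A:** "Statistical analysis will include paired t-test of quantitative measures such as VAS pain score, Oswestry Disability Index, PROMIS 29, and quantitative secondary outcomes". The only other technique named there is a regression analysis to look for correlates of outcome; no other test of change appears.
- **Outcomes, V.B:** VAS change ("Improvement in baseline in VAS from baseline at 6 months"), ODI and PROMIS-29 at 6 months are secondary. The primary outcome is a binary composite.
- **Loss, II.C:** "Assuming a 20 percent loss to follow up or study exit rate, fifty patients would be sufficient to achieve study aims". No time point is attached to the 20%.
- **Visits, II.E item 1:** "Patients included in the study return for follow-up visits at 7-14 days, 1, 3 months, 6, 12, 18, and 24months post-treatment", with "Primary endpoint will be 6 month time point". The V.D schedule marks VAS, ODI and PROMIS-29 at all seven post-treatment visits, so three sets of scores precede month 6.
- **Exit, II.D and II.K:** patients leave only at their own request, and opting out is to be discussed when an adverse event or post-procedural problem arises.

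**The concern.** A paired t-test of baseline against month 6 needs both values. A patient seen at 7-14 days, 1 month and 3 months who then leaves contributes nothing to the 6-month result, although those scores show how that patient was doing. The mean of the remaining pairs estimates the mean for all treated patients only if loss is unrelated to outcome.

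The protocol's own text makes outcome-related loss plausible: exit is the patient's choice and is raised when things go wrong. In a two-arm trial part of such a bias might cancel between arms; here nothing offsets it. At stake is the accuracy of the 6-month mean improvement and its interval.

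**Working it through.** **1. The plan's own figure.** Inputs from II.C: "Alpha 0.05, Beta 0.2, Power 0.8, Effect Size 0.5, two sided yielded sample size of 34 patients". Exact paired t-test power comes from the noncentral t distribution with n - 1 degrees of freedom and noncentrality 0.5 × √n. It is 0.795 at n = 33 and 0.808 at n = 34, so 34 reproduces. Allowing for 20% loss, 34 / 0.8 = 42.5, so 43 patients suffice. Enrolling 50 leaves 50 × 0.8 = 40 pairs, with power 0.869, and tolerates loss of 1 - 34/50 = 32%. Power is therefore not the issue. The calculation does show that loss is met by enrolling more patients.

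**2. Size of the bias in general.** Let p be the share lost and D the mean improvement of those who stay minus that of those who leave.

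Bias of the observed-pairs mean = p × D

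| D (mm VAS) | p = 20% | p = 10% |
|---|---|---|
| 5 | 1.0 | 0.5 |
| 10 | 2.0 | 1.0 |
| 20 | 4.0 | 2.0 |
| 30 | 6.0 | 3.0 |

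If good responders leave more often, D is negative and the bias reverses.

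**3. Simulation of what the earlier visits recover.** The protocol gives no SDs or correlations, so these are assumptions: 50 patients; baseline VAS 75 (SD 12); true 6-month fall 33 mm (6-month SD 25); correlation between post-treatment visits 0.6 to 0.8; loss after month 3, with odds multiplied by 2 or 3 per SD of 3-month pain. The comparator regresses the 6-month score on baseline and the three earlier visits and averages over all patients. For loss after month 3 this corresponds to the mixed-model estimate.

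- 20% loss: observed pairs overstate the fall by 1.4 to 3.0 mm; the estimate using earlier visits has bias of about 0. A repeat with baseline-to-follow-up correlation set at 0.3 gave 1.6 to 2.9 mm.
- 10% loss: the overstatement is about half, roughly 1 to 1.5 mm.
- Random 20% loss: neither estimate is biased. Standard errors, paired against repeated-measures, are 3.84 v 3.69 (r = 0.6), 3.76 v 3.55 (r = 0.7) and 3.89 v 3.55 (r = 0.8). The variance reductions are 1 - (3.69/3.84)² = 8%, 1 - (3.55/3.76)² = 11% and 1 - (3.55/3.89)² = 17%.

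**4. Stronger dependence, and loss driven by unseen scores.** A separate simulation assumed SD of change 20 to 30 mm, correlation 0.5 to 0.7, 20% loss and a steeper link between response and loss.

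| Loss depends on | Bias, observed pairs (mm) | Bias using earlier visits (mm) |
|---|---|---|
| Observed 3-month change | +2.3 to +4.9 | about 0 |
| Unseen 6-month value | +4.6 to +6.9 | +2.0 to +4.6 |

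The earlier visits remove the bias in the first case and only reduce it in the second.

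**The case against.** The strongest reply is that the protocol never says completers only and names no missing-data rule. V.A says what the analysis will include, which is not exhaustive, and a SAP that is not shown could add imputation or sensitivity analyses. That stands as far as it goes: the observed-pairs reading is an inference from the named test, and enlarging enrolment does not by itself fix an analysis set. But the test is named in two sections as the analysis of these measures. The point is that a stated method can be improved on data already scheduled, not that detail is absent.

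The effect is also modest. On the assumed inputs, 1.5 to 3 mm on a 33 mm fall is under one standard error (about 3.8 mm) and well below the 20 mm criterion in the primary composite. That stands too.

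A reader might infer more than the documents support:

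- *That 10 of 50 patients will be missing at month 6.* The 20% has no time point and follow-up runs to 24 months, so loss by month 6 may be smaller.
- *That every efficacy test is affected.* The outcomes here are secondary. The primary is a binary composite that a paired t-test does not analyse, and a model for mean change would not repair it.
- *That the earlier scores are thrown away.* Nothing restricts the paired t-tests to month 6, so those scores may be tested visit by visit. They are unused only in the 6-month estimate.
- *That a mixed model is simply unbiased.* It is so only if loss is explained by observed scores, as the second row of the last table shows. Comparing it with the paired t-test cannot check this, because the paired t-test makes the stricter assumption.

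**Conclusion.** The point holds as an improvement to a stated method for three secondary outcomes. With the paired t-test as written, 6-month improvement is overstated if patients doing badly leave more often. The assumed inputs give about 1.5 to 3 mm VAS at 20% loss and about 1 to 1.5 mm at 10%, with larger values if loss depends more steeply on response. If loss is random the cost is precision only: the repeated-measures variance is roughly 8 to 17% lower at 20% loss. All millimetre figures rest on assumed SDs, correlations and loss mechanisms, and the direction depends on who leaves. The sample size is adequate, and a large improvement would probably remain significant; what is affected is the accuracy of the reported mean. It should be changed before analysis, but it does not invalidate the study.

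**What to change.** In II.C and V.A, make the main analysis of 6-month change in VAS, ODI and PROMIS-29 a mixed model for repeated measures:

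- Responses: baseline, 7-14 day, 1-, 3- and 6-month scores, with visit as a factor.
- Covariance: unstructured, with a simpler structure named in advance if the model does not converge. Stopping at month 6 gives five time points and 5 × 6 / 2 = 15 covariance parameters. Using all eight time points would need 8 × 9 / 2 = 36, which is heavy for 50 patients.
- Report: the 6-month-minus-baseline contrast with its 95% CI.
- Supportive: keep the paired t-test on patients with both scores.
- Sensitivity: impute missing 6-month scores with a stated range of unfavourable shifts (delta adjustment), to show how far loss that depends on unobserved scores could move the result.

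The cost is wording and slightly more analysis work. No visits, data or patients are added, and the SPSS package named in V.A can fit the model. The analysis would rely on loss being explained by observed scores, which is a weaker assumption than the paired t-test makes. The power calculation for 34 pairs need not change. Handling of missing data in the binary primary endpoint is a separate matter.
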